## Measures

To test the mechanism of action for canine interaction in reducing social anxiety in adolescents, we will collect three levels of outcome data: a) self-reported experience (anxiety), b) autonomic physiological reactivity (heart rate), and c) cognitive performance (error rates on mental math task).

*Social anxiety.* The SAS-A will be used to assess overall level of social anxiety. The SAS-A was designed for use in adolescence and has been validated extensively across many samples and in multiple languages (e.g., Garcia-Lopez et al., 2011; La Greca & Lopez, 1998). The SAS-A contains 18 items that include three domains of social anxiety: fear of negative evaluation from peers, social avoidance and distress in new situations, and generalized social avoidance.

*Self-Report Experience:* Self-reported affective experience will be measured using the state scale of the State-Trait Anxiety Inventory (STAI; Spielberger et al., 1983), which is validated for use in adolescence and is commonly used with the TSST. The STAI state scale contains 20-items rated on a four-point scale, and has consistently demonstrated excellent reliability (ranging from  $\alpha = .86$  to  $.95$ ; Spielberger et al., 1983) and construct validity (Spielberger, 1989). Anxiety will be measured at six time points, during: (1) baseline, (2) anticipation (3) preparation, (4) speech, (5) mental math, and (6) recovery.

*Autonomic physiological reactivity:* Heart rate and electrodermal activity will be collected continuously using a clinical grade wristband sensor (Empatica E4; Garbarino et al., 2015).

*Cognitive Performance:* Cognitive performance during the social stressor task will be measured to understand how anxiety and AAI influence cognitive function. As recommended by existing research with the TSST paradigm (e.g., Simeon et al., 2007), we will measure cognitive performance during the mental arithmetic task by tracking the number of errors and lowest number reached by participants on the mental math task. Better performance will be characterized by fewer errors and reaching a lower number during serial subtraction.

*Demographic Characteristics:* In addition to the measures assessing the primary aims, we will also collect demographic covariate information from participants on age, sex, race/ethnicity, and current pet ownership.

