## APPROACH

The primary aim of this study is to test the mechanisms by which interacting with animals reduce anxiety (**Aim 1**). The second aim is to determine if the anxiolytic effect of contact with a dog is moderated by the level of pre-existing social anxiety in adolescents (**Aim 2**). To achieve these aims, we will complete a randomized, controlled laboratory experiment that uses a powerful and well-validated social evaluative stressor, the Trier Social Stress Task for Children (TSST-C; Buske-Kirschbaum et al., 1997). To understand and measure the anxiety reducing effects of interacting with animals, we will collect three levels of outcome data: a) self-reported experience (anxiety), b) autonomic physiology (heart rate), and c) cognitive performance (error rates on mental math task).

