The primary task all participants will complete is the Trier Social Stress Task for Children (TSST-C), which involves six distinct phases: baseline, anticipation, preparation, speech, mental math, and recovery (Buske-Kirschbaum et al., 1997). The TSST-C (as well as the adult version of the TSST) has been used extensively as a robust and reliable method for inducing social stress, and variants have been used in conjunction with animal interaction (e.g., Allen et al., 2002; Polheber & Matchock, 2013). The TSST-C was originally validated for use in 10-14 year olds (Buske-Kirschbaum et al., 1997), but the protocol used in this study is a specific adaptation validated for use in adolescents up to 17 years old (Stroud et al., 2009). The TSST-C involves a public speaking task and a mental arithmetic performance challenge. During the baseline rest period (20 minutes) rest period, participants will watch a science documentary (with no animal content) on a digital tablet. Participants will then be told about the task (anticipation). Then participants will have a 5-minute preparation period, and then they will be asked to speak on an academic topic for 5 minutes (e.g., give a plot summary and interpretation of a book of their choice). They will then be asked to complete a serial subtraction mental arithmetic task for 5 minutes. Per the Stroud et al. (2009) protocol, the serial subtraction task will be adjusted for age (13-14 year olds will subtract by 11s, 15-17 year olds will subtract by 17s). If an error is made, participants will be instructed to restart from the beginning.

Finally, there will be a 30-minute recovery period where they will continue to watch the science documentary. Throughout the TSST-C, participants will be asked to self-report their anxiety levels at each of the 6 phases and will wear a watch-like wristband (Empatica E4) to continuously measure heart rate data.

Compensation for the screening process will be a \$10 gift card (duration approximately 10 minutes). Youth who meet the eligibility criteria and who participate in the experiment will be compensated with a \$75 gift card (duration of the study approximately 2 hours, not including travel time to Tufts University).

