## *3. Performance Data*

Performance during the mental arithmetic portion of the TSST-C (number of errors and lowest number reached) will be recorded securely in REDCap.

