### **b) Protection Against Risks**

As noted above, there are minimal risks associated with this study. Although risks are minimal, we will provide participants with the PI's contact information should any questions or concerns arise, as well as provide contact information for mental health resources. We will also highlight the participant's right to discontinue his or her participation in any part of the study (including the TSST-C) at any time. If a participant becomes distressed during the TSST-C, the study will be stopped immediately, and the participant and his or her parent/guardian will be provided with contact information for a mental health professional.

As noted above, confidentiality of digital data will be maintained by assigning a four digit ID number to each participant that will be stored securely in REDCap. De-identified data files and video data files will be stored on a secure Tufts University server and will only be accessible by the PI and the co-investigators.

The animals participating in this study will be therapy dogs who are registered through Pet Partners® and members of Tufts Paws for People, reducing the risk of adverse events. The animals will always be accompanied by their handlers, who are required by Pet Partners to have their dogs on leash at all times while visiting and have been trained to advocate for their animals to ensure safety of all participants. As part of their Pet Partners training, all animal handlers have completed an 8-hr training course and their animals have passed a rigorous evaluation (with re-evaluation every 2 years) to meet training, safety, and health standards that protect both the animal-handler team and the people and facilities they are visiting. The animals are bathed 24 hours prior to participating in any program, and the teams are covered by comprehensive liability insurance through Pet Partners.

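### The cognitive outcome is called an error rate, but no number of responses is recorded, so the error count mixes accuracy with speed and can contradict its companion measure

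*Protocol*

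**What the plan says.** The Protocol's Approach section lists the third outcome level as "cognitive performance (error rates on mental math task"), and the opening of Measures uses the same label. Under Cognitive Performance in Measures, the quantities are obtained by "tracking the number of errors and lowest number reached by participants on the mental math task", and the direction of scoring is given as "Better performance will be characterized by fewer errors and reaching a lower number during serial subtraction". The section on Performance Data confirms what is stored: "number of errors and lowest number reached) will be recorded securely in REDCap". No section mentions a count of answers given.

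The task is described under Participants and Procedure: "They will then be asked to complete a serial subtraction mental arithmetic task for 5 minutes". The step is 11 for ages 13-14 and 17 for ages 15-17. On mistakes: "If an error is made, participants will be instructed to restart from the beginning".

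The section on Protection Against Risks adds that "If a participant becomes distressed during the TSST-C, the study will be stopped immediately". Nothing says how a shortened arithmetic task is scored.

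The SAP's Analyses section says only that cognitive performance is analysed by ANOVAs with condition as a factor and social anxiety as a centred continuous predictor. It does not name the metric, a denominator, or a way of combining the two measures.

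**The concern.** In a task of fixed duration, the number of errors depends on how often a participant answers as well as on how often an answer is wrong. Someone who answers slowly has fewer chances to err. If speed differs by condition or by level of social anxiety, the two predictors in the cognitive ANOVAs, a difference in error count need not reflect a difference in accuracy.

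There is a plausible route to such a difference. Participants in the third condition are encouraged to touch and interact with the dog during the tasks, those in the second may talk to it, and controls have a toy. The documents give no data on whether this changes speed.

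The second recorded measure does not resolve the matter. It also responds to speed, but in the opposite direction. A change in speed alone can therefore improve one cognitive measure and worsen the other, and the plan does not say which one carries the conclusion. That leaves the choice open until after the results are seen.

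**Working it through.** The documents give no figure for the cognitive outcome, so there is nothing to reproduce. The check has three parts.

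**1. Can the rate be recovered from the stored values?**

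Let *N* be responses, *E* errors, *s* the step (11 or 17) and *L* the longest error-free run.

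- Stored: *E*, and lowest number = start − *s* × *L* (because of the restart rule).
- Needed for errors per response: *E*/*N*.

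The lowest number gives *L* only. Many values of *N* are compatible with the same *E* and *L*, so *E*/*N* cannot be computed. The raw lowest number also depends on age: ten correct steps is a drop of 10 × 11 = 110 for a 13-year-old and 10 × 17 = 170 for a 15-year-old.

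**2. How do the two measures move when only speed changes?**

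Assumptions, none from the documents: each response is wrong with constant probability 0.20, and a full-speed participant gives 60 responses. Expected errors = *N* × 0.20. Longest runs and pairwise comparisons come from 100,000 simulated participants per setting.

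| Responses | Mean errors | Errors/responses | Mean longest run | Fewer errors than a 60-response participant | Lower number reached than a 60-response participant |
|---|---|---|---|---|---|
| 60 | 12.0 | 0.20 | 13.3 | – | – |
| 30 | 6.0 | 0.20 | 10.3 | 93% of pairs | 27% of pairs |
| 15 | 3.0 | 0.20 | 7.3 | 99.5% of pairs | 10.5% of pairs |

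For error probabilities of 0.10 and 0.30, the 30-response participant has fewer errors in 81% and 98% of pairs, and a lower number in 25% and 26%. A participant who is both slower and less accurate (30 responses, 0.30) still has fewer errors than one with 60 responses at 0.20 in 73% of pairs (means 9.0 and 12.0), but reaches a lower number in only 10%.

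**3. What would this do to a comparison of two arms?**

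Inputs: 25 per arm (Protocol and SAP). Assumed: 40 responses on average in the reference arm, mean error probability 0.15 in both arms, and between-person variation in speed (gamma-Poisson, shape 16) and in accuracy (beta distribution, concentration 10 to 50; a larger value means less spread). The test is a two-sided t-test at 0.05. Mean errors = mean responses × 0.15.

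| Slowing in one arm | Mean errors | Significant on error count | Significant on errors/responses |
|---|---|---|---|
| none | 40 × 0.15 = 6.0 | about 5% | about 5% |
| 20% | 32 × 0.15 = 4.8 | 13-25% | about 5% |
| 30% | 28 × 0.15 = 4.2 | 26-51% | about 5% |
| 50% | 20 × 0.15 = 3.0 | 71-96% | about 5% |

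The ranges reflect the assumed spread in accuracy. Accuracy is identical in both arms throughout, so every rejection above 5% comes from speed. At 50% slowing, the mean longest run falls from about 16 to about 10.5, so the companion measure points to harm while the error count points to benefit.

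**The case against.** The strongest reply is that the error count does not stand alone. Better performance is defined by fewer errors and also by reaching a lower number. A reader might infer from the missing denominator that anyone who slows down, freezes or is stopped is scored as performing better overall. The documents do not support that. Take 10 answers with 3 wrong against 60 answers with 6 wrong. The first participant's longest correct run is at most 7. The second has 54 correct answers in at most 7 runs, and 54/7 = 7.7, so at least one run has 8 or more. With the same start and step, the first participant is better on errors and necessarily worse on the lowest number. With large slowing, the second measure would usually contradict a false benefit. This part of the reply stands.

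It is also true that no passage says dogs slow answering or that anxious adolescents freeze. The slowing percentages are illustrations, and a claim that the plan favours the dog conditions would be conjecture. Nor does any passage say that a task stopped for distress is scored as it stands. What exists is a missing rule, which is different from a rule that rewards stopping.

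Finally, an error rate can be read as errors per 5-minute task, which the stored count does supply for those who finish. That softens the mismatch in naming. It does not separate accuracy from speed, and it fails for a task cut short.

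The reply does not show that either recorded measure isolates accuracy, or that the plan says what to conclude when the two disagree.

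**Conclusion.** The point holds in a limited form. Errors per response cannot be computed from the recorded fields. The raw count mixes accuracy with speed, and at equal accuracy the two recorded measures tend to move in opposite directions as speed changes. The SAP names neither as the analysed outcome and does not cover incomplete tasks.

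The first two statements follow from the task rules and the list of stored fields. The size is conditional: roughly 13-25% false positives on the count at 20% slowing rests on an assumed 40 responses, a 15% error probability that stays constant through the task, and the assumed spread between participants. If the conditions do not differ in speed, the rate stays near 5%.

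Severity is minor to moderate. Cognition is one of three outcome levels, but the SAP bases the sample size on heart rate and STAI and makes no power statement for cognition.

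**What to change.** - **Record** the total number of responses, correct plus incorrect, alongside errors. This can be scored live or tallied from the session video, provided that answers can be made out on the recording. Video coding is currently planned only for social referencing, so the tally must be added to the plan.
- **Analyse** errors divided by responses as the accuracy outcome, or model errors with log(responses) as an offset. Keep the raw count as descriptive.
- **Report** the lowest number reached as a separate measure, in steps completed, that is (start − lowest number) divided by 11 or 17, so that the age groups are on one scale.
- **State** in the SAP which measure carries the cognitive conclusion. For any task cut short, say that accuracy uses the responses given up to that point, and report the number of such tasks by condition.

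The cost is one extra data field, a sentence or two each in Measures and the SAP, and a short tally per session. No change to the task or the sample size is needed.

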Another possible mechanism for anxiety reduction is physical touch. Since the famous "wire mother" studies by Harlow & Zimmerman (1959), researchers have explored the effects of physical touch, though the topic remains relatively understudied (Field, 2010). Most touch research has focused on interpersonal touch between two humans (for review, see Gallace & Spence, 2010). Research has found touch can reduce the experience of pain (Mancini et al., 2014) and influence heart rate, even in young children (Fairhurst et al., 2014). In a hospital setting, touch can reduce anxiety and blood pressure (though these findings are moderated by gender; Whitcher & Fisher, 1979). Less research has looked at how touching animals can influence anxiety, but initial evidence suggests that physical contact with a dog may be an important component of the interaction (Vormbrock & Grossberg, 1988; though this research has significant methodological weaknesses). Increased physical touching of a dog is correlated with less of a cortisol response in children with attachment disorders during laboratory induced stressors (Beetz et al., 2012). The second mechanism we will test is whether physically touching an animal buffers anxiety above and beyond social support alone. Initial research has suggested that contact with an animal was associated with lower anxiety than social contact with a human friend (Polheber & Matchock, 2013), suggesting that physical touch may be an important additive factor for reducing anxiety.

In addition, there is a lack of research on whether AAIs benefit adolescents with social anxiety in particular. Although existing literature supports the scientific premise that animal contact can buffer anxiety, this effect has primarily been tested in healthy adults (Allen et al., 2002; Polheber & Matchock, 2013), children with attachment disorders (Beetz et al., 2012; Wedl et al., 2015), and children with autism spectrum disorder (O'Haire et al., 2015). Our secondary goal is to specifically test the effectiveness of AAIs for adolescents with varying levels of social anxiety (**Aim 2**).

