## Statistical Analysis Plan

### *Sample Size Calculation:*

To estimate the sample size, we used heart rate (HR) as the primary outcome and the STAI (state subscale) as the secondary outcome. There are no prior data with which to estimate the relative effect of the two intervention and control conditions on the proposed outcomes. Therefore, estimates were compiled from other research using HR as an indicator of stress response (e.g., Greenland et al., 1999). In this situation, the most conservative approach for sample size calculation is to assume a series of two-way tests. We used a mean of 75 beats per minute (bpm) with a  $SD$  of 12 bpm for baseline in all groups, assuming normal distribution, an equal number of subjects in each group, and a 0.05 significance level (alpha). With these assumptions, we will have 90% power to detect a difference of 12 bpm between any two treatment groups with 23 subjects per group, which we round to 25 per group for a total of 75 subjects in the three treatment groups. To determine the power for the STAI state subscale, based on the STAI normative data (Spielberger et al., 1983), we use a mean of 35.5 with a  $SD$  of 10.5. Using the same approach as above for HR, we will have 90% power to detect a difference of 10 between any two groups with a sample size of 25. All sample size and power calculations were performed using PASS 13 (Hintze, 2014).

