### *Analyses:*

To test our confirmatory hypotheses, we conducted two three-way analyses of variance (ANOVA) with either self-reported anxiety (STAI), autonomic reactivity (electrodermal activity [EDA] and heart rate [HR]) as the dependent variable. For these outcomes, there were two between-subjects factors, condition (social, social + physical, control) and social anxiety (SA; centered continuous predictor), and one within-subjects factor, time point (1, 2, 3, 4, 5, 6). We included baseline STAI, EDA, or HR at time point 1 as a centered continuous covariate. For cognitive performance, we conducted ANOVAs that treated condition as a between-subjects categorical factor and social anxiety as a centered continuous predictor.

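### The cognitive-performance models have no term for age band, although the subtraction step, and so the lowest number reached, is set by age

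*Protocol*

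**What the plan says.** - **Variables collected.** Protocol, Measures (Demographic Characteristics): the study will gather "demographic covariate information from participants on age, sex, race/ethnicity, and current pet ownership". No section says what role these variables have in the analysis.
- **The task.** Protocol, Participants and Procedure: the serial subtraction is adjusted for age, so that "13-14 year olds will subtract by 11s, 15-17 year olds will subtract by 17s". The task lasts 5 minutes, and an error sends the participant back to the beginning.
- **The score.** Protocol, Measures (Cognitive Performance): performance is measured by "tracking the number of errors and lowest number reached by participants on the mental math task". Fewer errors and a lower number count as better.
- **The cognitive model.** SAP, Analyses: "For cognitive performance, we conducted ANOVAs that treated condition as a between-subjects categorical factor and social anxiety as a centered continuous predictor". There is no term for age or step. The outcome is measured once, so it has no baseline value to adjust for.
- **The other models.** For STAI, EDA and HR the SAP has condition, social anxiety and time point, and adds: "We included baseline STAI, EDA, or HR at time point 1 as a centered continuous covariate".

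**The concern.** A correct answer moves an older participant down by 17 and a younger one by 11. Two participants with the same number of correct steps, in the same arm, therefore finish at different numbers because of their ages. This variation comes from the design, is known before randomization, and goes into the error term of the cognitive models. Unlike the other outcomes, the cognitive outcome has no pre-task value that could absorb part of it.

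The stake is the precision of the condition contrasts on one of the three levels of outcome data. There is also a smaller point of pre-specification: a variable labelled a covariate, with no stated role, leaves room to add it or leave it out once results are known.

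**Working it through.** **1. The plan's own figures.** The SAP sizes the trial on HR (difference 12, SD 12) and STAI (difference 10, SD 10.5), at alpha 0.05 and 90% power. Two-sample t-test power (two-sided, noncentral t) is 0.91 for HR at 23 per group and 0.91 for STAI at 25 per group. Both stated sizes reproduce. Neither uses covariates, and neither concerns the cognitive outcome, for which the SAP gives no power calculation.

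**2. How much variance age band could explain.** Inputs from the protocol: steps of 11 and 17. Assumptions: 40% of participants are 13-14; both bands start from the same number; the coefficient of variation (CV) of correct steps is 0.3 to 0.7 and equal in both bands. Distance descended is taken as step × number of correct steps, which simplifies the restart rule. Let r be the older band's mean number of correct steps relative to the younger band's. In units of the younger band's mean number of steps:

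- band means: m1 = 11, m2 = 17r; overall mean m = 0.4·m1 + 0.6·m2
- between-band variance: B = 0.4(m1 − m)² + 0.6(m2 − m)²
- within-band variance: W = CV²(0.4·m1² + 0.6·m2²)
- R² = B/(B + W)

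Example, r = 1 and CV = 0.5: m = 14.6, B = 0.4 × 12.96 + 0.6 × 5.76 = 8.64, W = 0.25 × (48.4 + 173.4) = 55.45, R² = 8.64/64.09 = 0.135.

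| Older band's correct steps | CV 0.3 | CV 0.5 | CV 0.7 |
|---|---|---|---|
| equal (r = 1) | 0.30 | 0.13 | 0.07 |
| 20% fewer (r = 0.8) | 0.10 | 0.04 | 0.02 |
| 35% fewer (r = 0.65) | 0.00 | 0.00 | 0.00 |

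The last row is nil because 17 × 0.65 = 11.05: the larger step and the fewer steps cancel.

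**3. Chance imbalance.** With 40% in the younger band, two arms of 25 differ by 20 percentage points or more in age-band share with probability about 0.19 (two independent binomials).

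**4. Effect on power.** The difference of 0.8 SD is an illustration and is not in the documents. The model is taken as condition, social anxiety and their interaction (the interaction is assumed), so error df = 75 − 6 = 69, or 68 with age band added. The variance of a pairwise contrast is multiplied by v = (1 − R²)(1 + 1/68), where the second factor is the average cost of estimating one more term. The noncentrality is 0.8/√(v × 2/25), tested two-sided at 0.05.

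| Model | v | Noncentrality | Power |
|---|---|---|---|
| No age term | 1.000 | 2.83 | 79.6% |
| Age band, R² = 0 | 1.015 | 2.81 | 79.0% |
| Age band, R² = 0.10 | 0.913 | 2.96 | 83.1% |
| Age band, R² = 0.20 | 0.812 | 3.14 | 87.2% |

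Break-even is where (1 − R²)(69/68) = 1, that is R² = 1/69, about 1.4%.

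**5. Three covariates instead of one.** Adding age, sex and pet ownership gives v = (1 − R²)(1 + 3/66). Power is 77.8% at R² = 0, 79.9% at 0.05 and 81.9% at 0.10. Break-even is R² = 3/69, about 4.3%.

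**The case against.** The strongest case against is that nothing here is an error. The protocol says the demographics will be collected, not that they will enter a model, so the SAP contradicts nothing. Randomization protects the comparison without them, and chance imbalance is already reflected in the standard error. The step is larger for older participants because the task is adjusted for age; if that adjustment equalizes the number reached, age band explains almost nothing, as the last row of the first table shows. The mechanical link also concerns the lowest number reached, and the documents do not show that the error count depends on age band. All of this stands. It limits the point to precision of uncertain size.

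A reader might infer more than the documents support:

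- *That every model loses precision without age, sex and pet ownership.* The HR, EDA and STAI models already adjust for the time-point-1 value, which takes up stable differences between people. A main effect that is constant over time also cancels from condition-by-time contrasts. No document gives a figure for what these variables would explain beyond that, and with three covariates there is no real gain until they explain more than about 4%.
- *That the Background calls for adjusting for sex.* Its remark, "though these findings are moderated by gender", concerns touch in a hospital setting and describes moderation. That would argue for an interaction with condition, not for a main effect.
- *That demographic covariates would cure a baseline affected by assignment.* The protocol has the dog present in all TSST-C phases and lists baseline among them, so the timing deserves a separate question. Adding covariates while keeping the time-point-1 term does not answer it.

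Finally, the SAP's Analyses section is in the past tense. If the analyses are complete, an added term can no longer be called prespecified.

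**Conclusion.** The point holds for the cognitive models only. The documents establish that the step depends on age, that the lowest number reached is a score, that age is collected, and that no cognitive model has a term for it. This is a missed gain in precision, not a bias or a contradiction, and it is minor.

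Its size rests on assumptions: the 40% share, a common starting number, the CV range, the relative number of correct steps, and the 0.8 SD difference. Under them, age band explains from about 0% to 30% of the variance in distance descended. The gain in power is about 3 points at 10% explained and 8 points at 20%, against a loss of about 0.6 points if it explains nothing. Because the possible loss is so small, the change is worth making without knowing where in the range the truth lies. The same cannot be said for sex and pet ownership, or for demographic terms in the HR, EDA and STAI models.

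**What to change.** In the SAP's Analyses section, add age band (13-14 versus 15-17, equivalently the subtraction step) as a main-effect covariate in the cognitive-performance ANOVAs. State in one sentence what role the remaining demographics have: descriptive only, or in a named sensitivity analysis. If the cognitive analyses have already been run, report the age-adjusted model as a sensitivity analysis and label it post hoc.

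The cost is two sentences of SAP text and one error degree of freedom. No new data are needed, and the sample size calculation is unchanged.
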